### 1. Aims of the Study

Aim 1: Implement and evaluate a remote optic nerve assessment (RONA) protocol using telemedicine to identify glaucoma-associated disease in at-risk rural patients using portable multimodal structural and functional assessment of the optic nerve and retina. Also assess for diabetic retinopathy, cataract, visual acuity impairment, and refractive error.

Aim 2: Identify and evaluate remediation strategies for the barriers to patient adherence with referral and follow-up appointments by comparing the effectiveness of financial incentives along with a validated patient education program versus a validated patient education program alone.

Aim 3: Investigate the cost-effectiveness of the telemedicine program in diagnosing glaucoma using RONA versus usual in-person care from a glaucoma specialist.

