### 2. Protocol

**Source Population**. This consisted of patients seeking healthcare at three FQHCs in north central Alabama. The three FQHCs are part of the Cahaba Medical Care Foundation, an Alabama-based FQHC. They care for a population of approximately 16,000 patients per year, including 58% who are African American, 38% White, and < 3% Hispanic. Among the active patients in these FQHCs, health insurance status is 25% Medicaid, 30% Medicare, 25% private insurance, and 20% uninsured. The study clinics are in rural Alabama towns: Centreville (Bibb County), Maplesville (Chilton County), and Marion (Perry County). This region of Alabama borders or is part of the region known as the Black Belt named for its rich black soil that supported cotton agriculture. In the 19th century, the agricultural workers were enslaved African Americans. The Black Belt consists of 9 of 10 of the poorest counties in the state. Poverty is directly link to health disparities in the Black Belt. Today this region's population is over 50% African American.

**Inclusion criteria.** Patients presenting at these clinics were eligible to participate if they had one or more risk factors for  $GAD^{79}$  and volunteered to participate: (1) African American or His-panic  $\geq$ 40 years of age; (2) White  $\geq$ 50 years of age; (3) anyone  $\geq$ 18 years of age with diabetes, (4) anyone  $\geq$ 18 years of age with a GAD; and (5) anyone  $\geq$ 18 years of age with a family history of glaucoma. All participants spoke and understood English.

**Exclusion criterion:** If patients did not complete written informed consent to participate, they did not participate.

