electronically transferred to a remotely located glaucoma-fellowship-trained ophthalmologist for reading and interpretation. With respect to visual field data, only HFA3 data were transferred since the other two field tests are not routinely used in standard of care in glaucoma assessments. The ophthalmologist made the following diagnostic judgments based on the screening in terms of the presence of the following conditions: glaucoma, glaucoma suspect, ocular hypertension, diabetic retinopathy, cataract, refractive error, or any other ocular conditions identified through the above screening data.

Diagnoses for GAD conditions are as follows. Ocular hypertension is defined as no glaucomatous appearing disc changes (described below), a normal visual field (described below), and statistically elevated IOP ≥23 mm Hg. Glaucoma suspect is defined as the presence of glaucomatous-appearing disc changes (de-scribed below), normal visual field (described below), and statistically normal IOP < 23 mm Hg. Glaucoma refers to the presence of glaucomatous appearing disc changes (de-scribed below) and an abnormal visual field (described be-low). A glaucomatous appearing optic disk is defined as evidence of excavation, neuroretinal rim thinning or notching, localized or diffuse retinal nerve fiber layer (RNFL) defect, or a between-eye asymmetry of the vertical cup disc ratio > 0.2. A glaucomatous visual field defect is defined as a reliable SAP Humphrey 24-2 field (defined as < 33% false-positives results, false-negative results, and fixation losses) that exhibits a pattern standard deviation outside of the 95% normal limits, or a glaucoma hemifield test outside of the 99% normal limits consistent with an RNFL defect pattern based on clinical review. A normal eye that meets none of these definitions of GAD is defined as not having glaucomatous-appearing disc changes and having a normal visual field and statistically normal IOP < 23 mm Hg (both described above). Diagnoses of DR were made based on the National Health Service Grading Classification System.80

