### 4. Statistical Analysis Plan

Demographic, socioeconomic, medical, and ocular factors were compared across groups who did and did not receive incentives for obtaining follow-up care using unpaired t-tests for continuous data and using the Fisher's exact test for categorical data. The proportion of individuals in each group who were recommended for a follow-up comprehensive eye exam and, among those individuals, the proportion who attended that exam was compared using chi-square tests. Given the demographic differences in the study groups, the impact of incentivization was evaluated using a subset of incentivized and non-incentivized patients matched on age, sex and race. The impact of COVID-19 on follow-up attendance was estimated by correlating the rate of COVID-19 deaths in Alabama obtained from the Alabama Department of Public Health and the average number of daily hospitalizations per month with the proportion of those attending follow-up referrals during each month of the study. P-values ≤ 0.05 (two-sided) were considered statistically significant.

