If you are using any medications for your eyes, please list the medications and describe how often your take them?	

03/20/2023 3:39pm

projectredcap.org

If you have ever had eye surgery or laser treatment related to any eye condition, please describe.	
Does anyone in your family have glaucoma?	○ Yes ○ No ○ Maybe, Not sure
If YES, who has glaucoma (relationship)?	
☐ Mother ☐ Father ☐ Sister ☐ Brother ☐ Daughte ☐ Grandfather ☐ Other	r □ Son □ Grandmother
Does anyone in your family have a history of blindness?	○ Yes ○ No ○ Maybe, Not sure
If YES, who has a history of blindness (relationship)?	
☐ Mother ☐ Father ☐ Sister ☐ Brother ☐ Daughte ☐ Grandfather ☐ Other	r 🗌 Son 🔲 Grandmother
END TIME for Ocular and Medical History	
	<del></del>
Warning: It has been over 30 minutes since the start time. Please check the start time and end time on this	Yes No (The time period is over 30 minutes.)

REDCap\* 03/20/2023 3:39pm projectredcap.org

SIGHT Page 1

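### Known glaucoma-associated disease (GAD) is an entry route, but the SAP does not separate known from newly found GAD, and controlled ocular hypertension can meet the normal-eye definition

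*Combined protocol and SAP*

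**What the plan says.** **Entry.** Section 2, Protocol (Inclusion criteria) makes patients "eligible to participate if they had one or more risk factors for" GAD, and one of the five routes is being at least "18 years of age with a GAD". The single exclusion is lack of consent: "If patients did not complete written informed consent to participate, they did not participate". Known or treated disease is not excluded.

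**Purpose.** Aim 1 is to implement and evaluate the remote optic nerve assessment (RONA) so as to "identify glaucoma-associated disease in at-risk rural patients". Aim 3 concerns the cost-effectiveness of the programme in diagnosing glaucoma.

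**Definitions** (Section 2, Telemedicine). Glaucoma needs disc changes and an abnormal field. Suspect needs disc changes, a normal field and IOP below 23 mm Hg. Ocular hypertension needs a normal disc, a normal field and IOP of 23 or more. For the remaining group, "A normal eye that meets none of these definitions of GAD is defined as not having glaucomatous-appearing disc changes", together with a normal field and IOP below 23. None of these has a clause for prior diagnosis or current treatment.

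**Data on prior disease.** The Medical and Ocular History form has tick-box options for high eye pressure and for glaucoma or suspect (one combined option), plus a free-text item: "If you are using any medications for your eyes, please list the medications". The ocular history is sent to the remote ophthalmologist.

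**Analysis.** Section 4 (SAP) compares baseline factors, referral and attendance between arms, and evaluates the incentive in a subset "matched on age, sex and race". It describes no GAD yield and does not mention prior GAD.

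**The concern.** A patient who enters because of a known GAD has not been found by the programme. If such patients are counted as identified by RONA, the proportion depends on how many known patients volunteered as well as on what the screening detected. The same count used as the number of diagnoses in Aim 3 would make cost per diagnosis look too favourable.

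The normal-eye definition raises a second problem, in the opposite direction. It rests on pressure as measured on the day, so a person whose known ocular hypertension is controlled can be tabulated as having no GAD.

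Aim 2 is also touched. Participants with GAD are recommended for follow-up, so known cases enter the attendance denominator. The arms were enrolled one after the other without randomisation. If the share of known cases among those referred differs between arms, and known cases attend at a different rate, matching on three demographic variables does not remove the resulting bias.

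**Working it through.** There is no planned figure to reproduce: the documents give no yield, no share of known cases and no attendance rate. The only design number is the goal of 500 per arm, which does not bear on this point.

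**1. Which known cases can become normal?** Apply the four definitions with IOP at or above 23, then below 23:

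| Disc changes | Field | IOP ≥ 23 | IOP < 23 |
|---|---|---|---|
| No | Normal | Ocular hypertension | Normal |
| Yes | Normal | No category | Suspect |
| Yes | Abnormal | Glaucoma | Glaucoma |
| No | Abnormal | No category | No category |

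Only the first row moves to normal. Known glaucoma keeps its label at any pressure, and an eye with disc changes and a normal field is a suspect once pressure is below 23. As an assumed example, if 10% of 1,000 participants had known GAD and 10-40% of those were controlled ocular hypertension, then 1,000 × 0.10 × 0.10 to 1,000 × 0.10 × 0.40 = 10 to 40 known cases would meet the normal definition.

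**2. How far does mixing move the yield?** Let k be the share already diagnosed, u the newly found rate among the rest, and s the share of known cases still classed as GAD. All three are assumptions.

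Pooled yield = k·s + (1 − k)·u. With s = 1:

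| k | u | Pooled | Pooled / u |
|---|---|---|---|
| 0.05 | 0.20 | 0.05 + 0.95 × 0.20 = 0.240 | 1.20 |
| 0.10 | 0.15 | 0.10 + 0.90 × 0.15 = 0.235 | 1.57 |
| 0.15 | 0.10 | 0.15 + 0.85 × 0.10 = 0.235 | 2.35 |

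The first and last rows are the extremes over k of 5-15% and u of 10-20%.

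Setting s = 1 ignores step 1. In the middle row, s = 0.9 gives 0.09 + 0.135 = 0.225 (ratio 1.50), and s = 0.7 gives 0.07 + 0.135 = 0.205 (ratio 1.37). Known cases would then be 0.09/0.225 = 40% and 0.07/0.205 = 34% of all GAD counted.

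**3. What could it do to Aim 2?** Bias in the attendance difference = (arm difference in the known share among those referred) × (attendance gap between known and other participants). With an assumed gap of 25 points (75% v 50%), an imbalance of 5 points gives 0.05 × 25 = 1.25 points and one of 15 points gives 0.15 × 25 = 3.75. With an imbalance of 10 points and a gap of 10-30 points, the bias is 1-3 points.

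For scale, assume 40-70% of 500 per arm are referred (200 to 350) and attendance is near 50%. The standard error of the difference is √(2 × 0.25/200) = 5.0 points down to √(2 × 0.25/350) = 3.8 points.

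**The case against.** - **No pooled yield is planned.** A reader might infer that the SAP chooses to report known and new cases together. It does not: Section 4 contains no Aim 1 yield at all. The mixing arises by omission, in whatever count is later drawn from the whole sample. The gap still needs closing.
- **Enrolling known cases fits the programme.** Aim 1 does not say undiagnosed, and the Background describes detection and management. So the inclusion criterion does not contradict the aim. What stands is that a claim about detection needs a denominator without prior disease.
- **The reader sees the history.** The ophthalmologist receives the ocular history and uses clinical judgement, so a treated ocular hypertensive may well be recognised. But the written definitions do not say how prior diagnosis or treatment is to be used. A label informed by history is also not a RONA detection.
- **Controlled known cases in general.** A reader might infer that the pressure cut-off turns any controlled known case into a normal one. The definitions do not support this; only ocular hypertension is affected. This effect lowers the pooled yield, so it partly offsets the inflation.
- **The Aim 2 bias is hypothetical.** Nothing in the documents shows that known patients attend more often or that their share shifted between arms. Eligibility criteria were the same in both arms. Under the 25-point gap the worst case is about one standard error. The SAP does compare ocular factors between arms, which would probably show an imbalance but would not adjust for it.

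**Conclusion.** The point holds in a limited form. People with known GAD are admitted, no stated analysis separates them from new cases, and the SAP defines no Aim 1 yield. A whole-sample GAD count therefore could not be read as a detection rate. For illustration, it would be 1.20 to 2.35 times the newly identified rate with 5-15% known (all flagged) and 10-20% new among the rest, and less where some known cases are classed as normal. These shares are assumptions. Misclassification as normal is confined to known ocular hypertension with a normal disc and field and measured IOP below 23 mm Hg. For Aim 2 the documents do not establish confounding by prior GAD. They leave it uncontrolled, at about 1-4 points if the assumed imbalance and attendance gap were to occur. This is a gap in reporting and adjustment, and cheap to close.

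**What to change.** In the SAP:

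1. Derive prior GAD (yes/no) from the intake forms: self-reported glaucoma or suspect, high eye pressure, or IOP-lowering medication.
2. Report GAD results by prior status. Base the detection claim, and any count of diagnoses used in Aim 3, on participants without prior GAD, with a 95% CI.
3. Tabulate known or treated ocular hypertension separately from normal. This is a reporting rule only and changes nothing in clinical management.
4. Add prior GAD as an adjustment covariate in the Aim 2 attendance comparison, and show its distribution by arm among those referred.

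No new data are needed, and little precision is lost. At the illustrative values, 900 of 1,000 participants without prior GAD and a 15% yield give a 95% half-width of 1.96 × √(0.15 × 0.85/900) = 2.3 points.

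The costs are a smaller headline yield, hand-coding of free-text medications, and reliance on self-report. The form also combines glaucoma and suspect in one option, so the two cannot be told apart by history.

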Study Design. This study had two arms. The protocol, as described below, was identical in both arms, except for the following. One arm consisted of participants not receiving any financial incentive for attending recommended follow-up care with an optometrist or ophthalmologist based on positive eye screening results. The other arm had a financial incentive, that is, participants recommended to attend a follow-up care exam with an optometrist or ophthalmologist received \$50 for attending the appointment. In the second arm, we confirmed with the eye care provider through the optometrist's or ophthalmologist's electronic medical records (EMR) whether the participant attended the follow-up appointment. We considered randomizing patients to each of the two arms. We decided not to use this approach because we were concerned that patients may talk among themselves (they live in small rural communities) about some receiving a financial incentive to attend recommended follow-up visits versus others not receiving a financial incentive. This was viewed as causing a potential conflict for patients in terms of their participating in the study and viewed as potentially unfair by patients. Thus, our approach was to first enroll half of the total number of patients in the non-financial incentive arm, and then when that was complete, to enroll the second half of the total number of patients in the financial arm. The goal was to enroll 500 patients in each arm.

**Protocol Measurements**. These are each described below. All were completed in a single visit to the FQHC. All eye and visual function measurements were performed on each eye separately. The clinical coordinators (certified ophthalmic technicians) collected all data including questionnaires.

**Demographic review.** Questionnaires obtained information on birthdate, gender, race, ethnicity, marital status, medical insurance status, transportation availability, education level, employment status, whether they received an eye examination in the past two years, reasons for not seeking an eye examination in the past two years, and contact information (address, phone number).

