**Self-reported clinical characteristics**. Questionnaires obtained information on the following: smoking status, family history of glaucoma or blindness, and ocular history of major chronic eye diseases or conditions. Family history of glaucoma was considered positive if a participant reported a glaucoma diagnosis for a first degree relative (parent, sibling, child).

Ocular screening. All measurements were completed under undilated conditions, as follows. (1) Distance visual acuity was assessed using a Snellen chart presented at 20 feet while participants wore whatever correction (if any) they were habitually wearing for distance. (2) Autorefraction was carried out with the QuickSee (PlenOptika Inc) or Retinomax (Nikon). (3) Intraocular pressure (IOP) was measured with the iCare portable rebound tonometer (iCare USA). A second measurement was taken if the IOP was > 21 mm Hg. If these 2 IOPs differed by more than 2 mm Hg, a third measurement was taken. If IOP was measured twice, the mean value was used as the IOP; if it was measured 3 times, the middle value was used. Participants with IOP ≥ 30 mm Hg were referred to an optometrist or ophthalmologist in our fast-track protocol: IOP > 30 mm Hg within 2 weeks; IOP > 35 mm Hg, within 1 week; and IOP > 40 mm Hg, an urgent referral within 1 day. (4) Visual field was assessed using three methods: the Humphrey Field Analyzer 3 (HFA3) using the Swedish Interactive Threshold Algorithm Fast screening strategy (Carl Zeiss Meditec), the Melbourne Rapid Fields, a tablet-based perimetry test (M&S Technologies), and the Alleye test (Oculocare Medical).

**Retinal imaging.** Spectral domain optical coherence tomography (SD- OCT) was performed using the Maestro2 (Topcon Medical Systems), measuring the thickness of the retinal nerve fiber layer of the optic nerve head and of the macula by a single widefield OCT scan measuring 12 ×9 mm (512 ×128 pixels). This encompassed both the macula and disc. The Maestro2 also provided high-resolution fundus photographs encompassing both the optic nerve and macula.

**Telemedicine.** All the above ocular screening data and retinal imaging, as well as the medical and ocular history and demographics (age, gender, race, ethnicity) were

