Each participant, the FQHC primary care provider, and their eye care provider (if they had one) received the final report about the ophthalmologist's screening-based diagnoses. These were sent out electronically within 14 days of the participant's screening visit date. The report contained diagnostic information on the conditions mentioned above plus visual acuity, IOP, recommended treatment, and whether a follow-up exam was recommended.

Recommendations from the telemedicine ophthalmologist. Participants whom the ophthalmologist clinically judged as normal were recommended to undergo an annual comprehensive eye examination on a routine basis. The following participants were recommended for a follow-up examination visit with an optometrist who was partnered with the FQHC (located in a separate office), or an ophthalmologist at the Glaucoma Service at UAB, the Lions Eye Clinic at UAB, or an ophthalmologist whose clinic was located in the FQHC geographic area: participants with 20/40 or worse visual acuity and/or with an IOP ≥23 mm Hg in either eye, as well as those with GAD (glaucoma, glaucoma suspect, or ocular hypertension), DR, and/or other ocular condition that the ophthalmologist viewed as needing to be examined in per- son. The FQHC staff scheduled

the appointment and communicated the details to the participant. The study coordinator followed up with the clinic where participants were scheduled for the follow-up examination to determine whether they actually attended the appointment by contacting the eye clinic and getting confirmation through the EMR.

Vision-Specific Health-Related Quality of Life. This was assessed using the National Eye Institute Visual Function Question – 9.81

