are mean (average, value.	
Final IOP (OS-left eye) Reading: If IOP(OS) were	
measured 3 times, use median; If measured twice, use mean value	-

03/20/2023 3:39pm

projectredcap.org

ar and a second and	
IOP greater than 30, subject requires FAST TRACK	
○ Yes ○ No	
FAST TRACK RECOMMENDATIONS	

 
○ FAST TRACK- Schedule with eye care provider within 1 Da
 
○ FAST TRACK- Schedule with eye care provider within 1 W
 
○ FAST TRACK- Schedule with an eye care provider within 2
 
	eek (IOP>35)
When is FAST TRACK subject scheduled for eye exam?	
	(Date and Time)
Where is FAST TRACK subject scheduled for eye exam? (Date and Time)	

 
UAB Department of Ophthalmology
 
UAB Lions Eye Clinic
 
[name], OD Centreville
 
Own eye care provider ( get record release)
 
	
End Time for IOP	
Warning: It has been over 30 minutes since the start time. Please check the start time and end time of IOP.	Yes No (The time period is over 30 minutes.)
Vision Screening Failure	
Did subject meet any of the below criteria (Check all that ap	ply):
☐ 20/40 or worse in either eye ☐ IOP > OR equal to 23 mmHg	
Name of referral doctor or practice	

REDCap\* 03/20/2023 3:39pm projectredcap.org

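### Was follow-up attendance confirmed through medical records only in the incentive arm, and over a different period?

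*Combined protocol and SAP*

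**What the plan says.** The Study Design paragraph opens its account of the two arms with "The protocol, as described below, was identical in both arms, except for the following". Three things come next: no payment in one arm, $50 for attending the follow-up visit in the other, and the sentence beginning "In the second arm, we confirmed with the eye care provider through the" practice's EMR. The second arm is the incentive arm, because "our approach was to first enroll half of the total number of patients in the non-financial incentive arm" and the incentive arm came afterwards. The goal was 500 patients per arm.

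The paragraph on recommendations from the telemedicine ophthalmologist says that the FQHC staff made the appointment. The study coordinator then established whether the participant came, "by contacting the eye clinic and getting confirmation through the EMR". No arm is named there.

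The Statistical Analysis Plan compares, between groups, the proportion of referred participants who attended, using a chi-square test at two-sided 0.05. It evaluates the incentive in a subset matched on age, sex and race, and correlates monthly attendance with COVID-19 measures.

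None of these places says whether a rescheduled or late visit counts, or when the record was checked.

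**The concern.** Two features look troublesome together.

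First, an exception list that contains outcome verification suggests that the outcome was measured differently in the two arms. If incentive-arm visits were confirmed in the record and first-arm visits were not, some first-arm visits could be missed. The incentive would then look better than it is, and matching on age, sex and race would not correct that.

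Second, the arms are consecutive. If all records were checked on one calendar date, and visits counted whenever they happened, the first arm would have had longer to accumulate them. Stated time limits for a referral visit exist only for participants with high pressure who "were referred to an optometrist or ophthalmologist in our fast-track protocol". The other stated interval concerns the screening report: "These were sent out electronically within 14 days" of the screening visit. In the forms supplied, the appointment-date field is the fast-track one ("When is FAST TRACK subject scheduled for eye exam"), while the item for other screening failures reads "Name of referral doctor or practice".

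At stake is whether part of the Aim 2 difference reflects measurement and not behaviour, in a comparison that is already non-randomised.

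**Working it through.** **Step 1. Which text governs verification?** The plan gives no figure to reproduce here, so the places are set side by side.

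| Place | Content | Arm named? |
|---|---|---|
| Study Design | EMR confirmation, directly after the $50 payment | Second arm |
| Recommendations paragraph | Coordinator contacts the clinic and confirms through the EMR | None |
| SAP, group comparison | Proportion attending among those referred, each group | Both needed |
| SAP, COVID-19 analysis | Proportion attending in each study month | Both needed |

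The Study Design sentence does not say that the first arm went unchecked or was checked in another way. Payment depended on attendance, so confirming attendance is a natural thing to mention beside the payment. The recommendations paragraph sets out the full procedure for referred participants in general. Because the arms ran in sequence, the months in which only first-arm participants had been enrolled have no monthly attendance figure unless first-arm attendance was recorded. The reading under which all four places agree is one procedure for both arms.

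**Step 2. What is open on timing?** The recommendations paragraph defines the outcome by the scheduled appointment. Elapsed time can bias the comparison only if (a) late or rescheduled visits were counted and (b) the time from referral to record check differed between arms. The documents establish neither.

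**Step 3. What do the forms show?** The supplied forms are screening-day forms and break off at item 4 of the nine-item vision questionnaire. The satisfaction questionnaire described in the Protocol is not among them either. The absence of a general appointment-date field in this extract is therefore not evidence about the plan.

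**Step 4. How much misclassification would matter?** Inputs: two-sided 0.05 (SAP); 500 per arm (enrolment goal, used as a ceiling on the number referred). Assumptions: 300 or 150 referred per arm as alternatives, and attendance of 30% to 70%. One arm stays at the assumed attendance and the other is moved by *k* participants. With *n* per arm and pooled proportion p̄, the Pearson statistic without continuity correction is

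χ² = (k/n)² / [p̄(1 − p̄) × 2/n].

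Example: n = 500, 250 attending against 281, k = 31. Then p̄ = 531/1000 = 0.531, and χ² = 0.062² / (0.531 × 0.469 × 0.004) = 0.003844 / 0.000996 = 3.86, p = 0.0495. With k = 30, p = 0.057.

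Smallest k giving p ≤ 0.05 (moved down / moved up):

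| n per arm | 30% | 50% | 70% | Range in points |
|---|---|---|---|---|
| 500 | 28 / 30 | 31 / 31 | 30 / 28 | 5.6 to 6.2 |
| 300 | 22 / 23 | 24 / 24 | 23 / 22 | 7.3 to 8.0 |
| 150 | 15 / 17 | 17 / 17 | 17 / 15 | 10.0 to 11.3 |

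These are general detection thresholds for any misclassification. They do not estimate an error that occurred. They also concern the full-group test; the size of the matched subset is not given.

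**Step 5. Could a systematic timing difference reach that size?** Under assumption, yes. Suppose that 70% eventually attend, with exponential time to visit of mean *m* months, so that the proportion seen by month *t* is 0.7 × (1 − e^(−t/m)). For m = 3, checks at 6 and 12 months give 60.5% and 68.7%. For m = 6 they give 44.2% and 60.5%. The gaps are 8.2 and 16.3 points with no true effect. Nothing in the documents supports the 6-against-12-month contrast, the 70% or the exponential form, so this shows only that the mechanism is possible.

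**The case for a change.** The strongest case for action is that the conflict is literal and both texts are current. A list of exceptions to a common protocol includes EMR confirmation for one arm, and a reader cannot prove from the documents that the sentence concerned payment only. The rule for late visits is missing from the visible text. Sequential enrolment makes unequal look-back a plausible hazard, and Step 5 shows that a systematic difference could exceed the thresholds in Step 4. The suggested remedy is to count attendance within one common period from referral in both arms.

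The drafting is indeed loose, and the late-visit rule is indeed unwritten. The case for changing the analysis is weaker. A common period chosen now would be post hoc, since the document is written in the past tense. Its length would have no basis in the plan, and it would require visit dates from several outside practices. It could also introduce bias: the SAP itself treats COVID-19 as a possible influence on attendance, and the arms ran at different times. A fixed cut-off could therefore turn pandemic delay into non-attendance more often in one arm than in the other. That cost is concrete, whereas the unequal look-back it would guard against is not shown. Such a period would be at most a sensitivity analysis.

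**Conclusion.** The concern does not call for a change to the plan. The first part is a drafting slip: on the reading that reconciles the Study Design paragraph, the recommendations paragraph and the SAP, attendance at the scheduled appointment was checked in the same way in both arms, and the bias from this source is zero. The second part is a missing detail that analysts would ordinarily fill by treating rescheduled visits alike in both arms and reporting when the records were checked.

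No bias can be computed, because the documents give no attendance rate, number referred, late-visit count or check date. Starting from equal attendance, a net 28 to 31 participants at 500 per arm, or 15 to 17 at 150 per arm, would have to be misclassified before the full-group test became significant, so a few late visits would not do it. This rests on the assumed attendance of 30% to 70% and on the recommendations paragraph applying to both arms. If first-arm attendance was in fact established differently, or over a clearly different time, that would be a limitation of the Aim 2 comparison to disclose. The documents do not show that it was.

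### At a final IOP of exactly 30 mm Hg the protocol's fast-track rule includes the participant, but its lowest time tier and the form's gate label do not

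*Combined protocol and SAP*

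**What the plan says.** In the protocol's Ocular screening paragraph, item (3) on intraocular pressure, one sentence sets both entry to fast-track and its deadlines: "Participants with IOP ≥ 30 mm Hg were referred to an optometrist or ophthalmologist in our fast-track protocol: IOP > 30 mm Hg". The lowest deadline reads "IOP > 30 mm Hg within 2 weeks". The next two tiers are above 35 (1 week) and above 40 (1 day). The same item defines the final IOP: a second reading if the first exceeds 21, the mean of two readings, and the middle of three if the first two differ by more than 2.

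The form Vision Screening Snellen And IOP Results has fields for each eye's final value (for example "Final IOP (OS-left eye) Reading"), followed by a Yes/No item: "IOP greater than 30, subject requires FAST TRACK". Further down, under Vision Screening Failure, the form lists "IOP > OR equal to 23 mmHg".

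Ordinary referral is covered separately, in the paragraph on the telemedicine ophthalmologist's recommendations: follow-up is recommended for those "with an IOP ≥23 mm Hg in either eye", among other criteria.

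**The concern.** A participant at exactly 30 meets the entry condition but matches none of the three stated tiers. Within the protocol alone, most readers would assign the 2-week limit. The form does not support that reading, because its label would leave the participant out of fast-track altogether. The form also spells out equality at 23 mm Hg, so its strict wording at 30 cannot simply be taken as loose shorthand for at least 30.

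What is at stake is the deadline. Ordinary referral at 23 or above still applies, but the protocol states no time limit for that appointment, and the ophthalmologist's report may take up to 14 days. A referral that waited for the report could use up the whole 2-week fast-track window before anything was booked.

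**Working it through.** The plan states no figure to reproduce; the check applies each rule at and around its boundaries.

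**Inputs.** Protocol, Ocular screening: entry ≥ 30; tiers > 30, > 35 and > 40; the averaging rule. Form: gate > 30; reading range 1 to 60. Protocol, recommendations paragraph: ordinary referral ≥ 23. Protocol, Study Design: 500 per arm.

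**Step 1: the rules side by side.**

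| Final IOP (mm Hg) | Entry ≥ 30 | Tier stated | Form gate > 30 | Referral ≥ 23 |
|---|---|---|---|---|
| 29.5 | no | none | no | yes |
| 30 | **yes** | **none** | **no** | yes |
| 30.5 | yes | 2 weeks | yes | yes |
| 35 | yes | 2 weeks | yes | yes |
| 35.5 | yes | 1 week | yes | yes |
| 40 | yes | 1 week | yes | yes |
| 40.5 | yes | 1 day | yes | yes |

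The rules disagree only at 30. The values 35 and 40 each fall in the tier below and cause no gap.

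**Step 2: can a final value of 30 occur?** Assume whole-number readings from 1 to 60 (the form gives only the range). Two readings average 30 with no third reading needed for (30, 30), (29, 31) and (31, 29). Three readings give 30 whenever the middle one is 30. So it can.

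**Step 3: how many final values are affected?** Under the same assumption the possible final values are the 60 integers plus the half-values from 21.5 to 59.5, of which there are 39: 60 + 39 = 99 per eye. One of the 99 shows the conflict.

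**Step 4: two eyes.** A fellow eye above 30 triggers both the tier and the gate, so the conflict needs the higher eye to be exactly 30. Of the 99 × 99 pairs of values, 2 × 99 − 1 = 197 have 30 in at least one eye. There are 39 values at or below 30 (30 integers and the 9 half-values from 21.5 to 29.5), so 2 × 39 − 1 = 77 pairs have a maximum of exactly 30. These are counts of combinations, not probabilities.

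**Step 5: illustrative number of people.** Planned total 2 × 500 = 1,000. If the share with a higher-eye IOP of exactly 30 is 0.1%, 0.5% or 1%, the count is 1,000 × 0.001 = 1, 1,000 × 0.005 = 5, or 1,000 × 0.01 = 10. The share is an assumption; nothing in the documents supports one value over another.

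**The case against.** The strongest reply is that the protocol sentence resolves itself: someone at 30 is in fast-track and not above 35, so 2 weeks is the only sensible deadline. That is fair for the protocol read alone, and it leaves the form label as the only real contradiction.

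The form evidence is also limited. The IOP limit on its 2-week option is cut off in the available text, the gate is a Yes/No item with no legible branching, and nothing shows how anyone at 30 was handled. The label says only IOP, so staff who saw readings of 29 and 31 might have ticked Yes. The conflict in wording stands regardless, because the label is written in words and is legible.

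A participant at 30 is not lost. The ≥ 23 rule applies, and the form's own ≥ 23 item and its field "Name of referral doctor or practice" could start a referral on the screening day. This is correct and is the main reason the point is minor, but neither route states an appointment deadline.

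Finally, the number of people affected is not evidenced, and screening is described in the past tense, so editing the wording protects nobody already enrolled. Both points stand. They argue for the query described under the fix and do not remove the inconsistency.

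**Conclusion.** The concern holds and is minor. At a final IOP of exactly 30 mm Hg, protocol entry says fast-track, the form's gate label says not, and no deadline is explicitly stated. It affects one boundary value, and only participants whose higher eye is exactly 30. The figure of 1 to 10 people among 1,000 rests wholly on an assumed share of 0.1% to 1%. No missed deadline or harm is shown. The SAP's comparison of follow-up attendance does not depend on the fast-track tier and does not change.

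**What to change.** Use ≥ 30 throughout. The ≥ in the entry clause could itself be the slip, but including 30 is the safer direction. In the protocol, set the first tier to IOP ≥ 30 mm Hg within 2 weeks. On the form, change the gate to greater than or equal to 30, and align the 2-week option if it differs.

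Then run one query: participants with a final IOP of exactly 30 in either eye and neither eye above 30. List the fast-track answer, the tier chosen and the entry under "When is FAST TRACK subject scheduled for eye exam". Where no fast-track date was recorded, use the eye clinic's EMR confirmation to check that they were seen promptly. The protocol describes that confirmation as establishing attendance and does not say that a visit date was recorded, so timing may need a further look-up. If the query finds nobody, the matter closes.

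The cost is one operator in the protocol, one on the form (two if the 2-week option also needs it), and a query mainly on fields already collected. The only downside is possibly a few more fast-track appointments if the form is used again.
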